#### 3.1. Justification for Use of Placebo:

The use of a placebo is necessary to control the psychological effects of caffeine supplementation, ensuring that observed effects were solely due to the active ingredient. By employing a Quadruple-blind design, the placebo also would help eliminate bias.

## 3.2. Justification for Using Biological Samples:

Biological samples are essential for objectively assessing the physiological effects of caffeine supplementation. They provide measurable biomarkers, reducing reliance on self-reported data and enhances the study's accuracy and reliability.

28.02.2025

## 4. Study Method, Patient Recruitment, Data collection

### 4.1. Study Design:

This study will be a randomized, quadruple-blinded, placebo-controlled trial with parallel-group allocation

#### 4.2. Study Duration:

Six months.

#### 4.3. Study Setting and Population:

The study will be conducted at the Gastroenterology Clinic, University Medical Unit, Colombo North Teaching Hospital, Ragama, Sri Lanka. Participant recruitment and follow-up will be done at this venue. Medical investigations and scanning will be done at the Colomb North Teaching Hospital, Ragama which has a SLAB accredited laboratory and a calibrated liver fibro scan. All patients with ultrasonically proven fatty liver disease will be recruited for the study.

#### 4.3.1. Inclusion Criteria

- Both male and non-pregnant, non-lactating female patients aged 18 65 years who provide written informed consent before starting the study
- Patient diagnosed with type 2 diabetes based on American Diabetes Association (ADA) definition or who only take oral antidiabetic drug.
- CAP score >263
- Fulfilling 2/3 USS criteria for fatty liver

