#### Patient Selection: Screening and eligibility assessment

- Advertisement about the details of the study and contact number of PI will display in all three languages (Sinhala/English/Tamil)at the Liver Clinic of Gastroenterology & Hepatology Department at CNTH-Ragama .Volunteering participants will contact PI and they will asked to come to Faculty medicine, University of Kelaniya, and they will approach by a trained medically qualified research assistant. First, the patients will be provided detailed information about the study and will be given an opportunity to discuss their concerns/questions in their preferred language (Sinhala/English/Tamil) with the medical investigator.
- Once the patient is satisfied with the information given, he/she will be screened for eligibility to participate in the trial. Informed written consent will be obtained from all patients with ultrasonically proven fatty liver disease for the eligibility assessment.
- All consenting patient's eligibility assessment for inclusion and exclusion criteria will be recorded in CRF by RA and reviewed by medical investigator in the team.
- Patients complied with inclusion exclusion criteria will be recruited to study and patients
  who are not eligible will be directed to Liver Clinic of Gastroenterology & Hepatology
  Department at CNTH-Ragama to receive standard care of treatment.

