#### Laboratory investigations

Serum fasting plasma glucose, Lipid profile, Liver enzymes will be done to assess the
baseline fasting blood glucose for recruitment into the study to comply with inclusion
criteria. Serum HCG will be tested for female participants to exclude pregnancy.
Abdomen ultrasound scan will be performed to assess eligibility to the study.

28.02.2025

After recruitment baseline testing will be done for HbA1c, serum Insulin level, fasting
plasma glucose, Lipid profile, Liver enzymes. Serum creatinine, full blood count, serum
electrolytes and urine analysis will be done for safety assessments.

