#### Ultrasound and Fibro scan

At the baseline Ultrasound scan will be performed to confirm the diagnosis of NAFLD.
 After recruitment at the baseline and at the end of six months a fibro scan will be done to assess the efficacy parameters. The ultrasound and fibro scan will be done at North Colombo Teaching hospital

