## 5.1. Lifestyle modification and standard care during the study period

There is currently no approved pharmacological treatment which can reverse NAFLD or control disease progression. Hence current treatment strategies are focused on lifestyle modifications. All patients in the two groups will receive standard diet modification and exercise and physical activity recommendations according to Clinical Practice Guidelines developed by Sri Lanka College of

28.02.2025

Endocrinologists, Sri Lanka society of Gastroenterology, 2019. However, management of comorbid conditions such as diabetes and hypertension will be as per routine hospital practice based on guidelines. If patients are already on pharmacological treatment for NAFLD, such patients will not be recruited to study.

Before recruitment all participants will be made aware of the required lifestyle modification during the study period as per standard management schedule.

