#### 5.5. Follow up assessment

The recruited patients will be advised to come for monthly assessments and will be asked to attend the nearest hospital, if they develop any complications and inform the study team of such incidence.

The degree of adherence to prescribed lifestyle changes and diet will be recorded at the baseline and monthly follow-up visits. Physical activity and alcohol consumption will also be monitored at the baseline and monthly follow-up visits.

Anthropometric measurements, physical examination and vital sign measurements (BP, HR, RR etc..) will be monitored at the baseline and each monthly visit. Details on concomitant medications will be recorded in monthly visits.

Liver profile, Lipid profile, Full blood count, Serum creatinine, fasting blood glucose, HbA1c, serum insulin, serum electrolytes and urine analysis and serum insulin will be investigated at the baseline, at 3 months and 6 months.

Fibro scan will be done at the baseline and after 6 months at the completion of the study.

The details of items which will be measured on every visit are described in Table 2.

Table 2: Summary of follow up

	Enrolment	Allocation 1	Subsequent visits							
TIME POINT		0	1 st	2 nd	3 rd	4 th	5 th	6 th		
			mont	mont	month	mont	month	mont		
			h	h		h		h		
ENROLMENT										
Eligibility screen	×									
Informed consent	×									
Allocation		×								
INTERVENTIO										
NS										
caffeine or		×	×	×	×	×	×			
placebo										
ASSESSMENTS										
Medical history	×	×	×	×	×	×	×	×		
taking										
AUDIT	×	×	×	×	×	×	×	×		
FFQ and IPAQ	×	×	×	×	×	×	×	×		

Height, weight			×	×	×	×	×	×
and waist								
circumference								
Blood pressure	×	×	×	×	×	×	×	×
Physical examination 	×	×	×	×	×	×	×	×
USS scan	×							
Fibro scan		×						×
FBG	×	×			×			×
Fasting serum insulin		×			×			×
HCG only female	×							
Serum HbA1c		×			×			×
Lipid profile	×	×			×			×
Liver enzymes	×	×			×			×
Total bilirubin	×				×			×
Serum creatinine		×			×			×
Serum electrolytes		×			×			×

FBC	×		×		×
UFR	×		×		×

28.02.2025

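### CAP above 263 is an entry criterion, but the first Fibroscan is scheduled after recruitment with no check before allocation, and the diabetes criterion contradicts the stated population

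*Protocol*

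**What the plan says.** **CAP criterion and the scan schedule**

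- Section 4.3.1 lists "CAP score >263" among the inclusion criteria, with no timing attached.
- Section 4.5 makes eligibility the gate to recruitment: "Patients complied with inclusion exclusion criteria will be recruited to study".
- Section 4.6 (laboratory investigations) gives the eligibility tests as fasting glucose, lipids, liver enzymes and, in women, HCG. On imaging it says "Abdomen ultrasound scan will be performed to assess eligibility to the study". The enrolment row of Table 1 lists the same kinds of blood test.
- Section 4.6 (ultrasound and Fibroscan) says "After recruitment at the baseline and at the end of six months a fibro scan will be done to assess the efficacy parameters".
- Section 5.5 repeats the timing: "Fibro scan will be done at the baseline and after 6 months at the completion of the study". Table 2 puts the eligibility screen and the ultrasound in the enrolment column. It marks Fibroscan only at allocation (time 0) and month 6.

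**Diabetes criterion and the population**

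- Section 4.3.1 also lists "Patient diagnosed with type 2 diabetes based on American Diabetes Association (ADA) definition or who only take oral antidiabetic drug".
- Section 4.3 says "All patients with ultrasonically proven fatty liver disease will be recruited for the study".
- The title refers to MASLD, and the hypothesis (2.1) and primary objective (2.2) to NAFLD patients. None of them has a diabetes condition. Section 5.1 treats diabetes as one example of a comorbid condition.

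**The concern.** An entry criterion works only if it can be measured when entry is decided. Here the instrument that measures CAP is first used after that decision, and its stated purpose is efficacy, not screening. The protocol does not say that the CAP result is looked at before a bottle number is given, or what happens to a recruited patient whose CAP is 263 or lower. The modified intention-to-treat rule in 4.8 depends only on having a follow-up assessment, so it does not settle the matter either. The variable left unchecked is also one of the three primary endpoints in 2.4.

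The population statements raise a different problem. Depending on which section is followed, the trial enrols only patients with type 2 diabetes or all patients with fatty liver on ultrasound. The diabetes criterion is itself unclear. Joined by *or*, a diagnosis of type 2 diabetes is enough whatever the treatment, and the oral-drug clause then restricts nothing among diagnosed patients. Two screeners could apply the list differently, and it would be unclear to whom the result applies.

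**Working it through.** **1. Order of events.**

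| Step | Where stated | CAP available? |
|---|---|---|
| Eligibility screen: bloods and ultrasound | 4.5, 4.6, Table 1, enrolment column of Table 2 | No |
| Recruitment of those who meet the criteria | 4.5 | No |
| First Fibroscan, for efficacy | 4.6, 5.5, allocation column of Table 2 | Yes, from here |
| Allocation | 4.7, allocation column of Table 2 | Order relative to the scan not stated |

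Every section that times the first scan puts it after eligibility has been decided. None fixes its order relative to allocation within the time-0 visit.

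**2. The plan's sample size.** Section 4.4 gives SD 5, difference 3, two-sided alpha 0.05, 80% power and 20% dropout. The standard two-sample formula is

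n per group = 2 × SD² × (1.96 + 0.84)² / difference² = 2 × 25 × 7.84 / 9 = 43.6, rounded up to 44.

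Allowing for dropout, 44 / 0.80 = 55 per group, 110 in total. This matches the plan. The standardised difference is d = 3/5 = 0.6.

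**3. Power with 44 evaluable per group.** Using the normal approximation, power = Φ(d × √(n/2) − 1.96):

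Φ(0.6 × √22 − 1.96) = Φ(0.854) = 80.4%.

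**4. If a share f of those randomised has CAP of 263 or lower.** The documents give no value for f. I assume 5%, 10% and 20%.

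- Removed: n = 44 × (1 − f), d = 0.6.
- Kept, with no effect at all in them (worst case): n = 44, d = 0.6 × (1 − f).

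| f (assumed) | Number of 110 | n if removed | Power if removed | d if kept | Power if kept, worst case |
|---|---|---|---|---|---|
| 5% | 5.5 (about 6) | 41.8 | 78.3% | 0.57 | 76.2% |
| 10% | 11 | 39.6 | 76.1% | 0.54 | 71.7% |
| 20% | 22 | 35.2 | 71.1% | 0.48 | 61.5% |

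**5. Population.** No arithmetic applies. Section 4.3.1 makes diabetes status a condition of entry. Section 4.3 recruits all patients with fatty liver on ultrasound. The title and 2.1 set no diabetes condition. If the list in 4.3.1 is applied as a whole, the sentence in 4.3 is wrong; if 4.3 is followed, the criterion is not being applied. The two cannot both hold.

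**The case against.** The strongest reply on CAP is that the protocol separates enrolment from allocation. Table 2 puts Fibroscan and allocation at the same visit, the 4.6 text says after recruitment and not after randomisation, and 4.7 randomises only eligible participants. A site could therefore scan first, read CAP, and withhold the random number if the criterion fails. This stands in part. A reader might infer that ineligible patients are bound to be randomised, and the documents do not support that. What remains is that no sentence requires the check, and 4.5 and 4.6 treat eligibility as already settled before the scan.

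A reader might also infer that removing such patients after randomisation would bias the comparison. The documents give no reason to think so. The exclusion would rest on a value measured before treatment, under blinding, with the same threshold in both arms. It would cost precision but would not by itself distort the contrast.

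The power figures are open to challenge, and fairly. The share is assumed, 4.4 does not say which endpoint or unit its SD and difference refer to, and no effect at all in those kept is a worst case. The dilution argument concerns CAP; nothing in the protocol says that patients with low CAP could not change on LSM or FIB-4.

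On population, entry criteria narrower than a title are ordinary, and 4.6 measures fasting glucose at screening with the inclusion criteria in mind. This suggests that a glycaemic criterion is intended. It does not remove the flat contradiction with 4.3, nor does it clarify the *or*.

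Finally, the bar on prior drug treatment in 5.1, "If patients are already on pharmacological treatment for NAFLD, such patients will not be recruited to study", is missing from the list in 4.3.2. A reader might infer that such patients could slip in. The rule is explicit and binds where it stands, so its placement is an editorial matter only.

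**Conclusion.** The concern holds on two counts. First, on the stated schedule the CAP criterion cannot be applied when eligibility is decided, and nothing requires it to be applied before allocation, so patients who fail it can be randomised. How many is unknown. For an assumed 5-20% share, with d = 0.6 and 44 evaluable per group, power falls from about 80% to about 78-71% if they are removed, or to about 76-61% if they are kept and have no effect. The defect does not depend on these figures; they only indicate what it could cost. Second, the protocol contradicts itself on whether type 2 diabetes is required, so the population to which the result applies is not fixed. Eligibility belongs in the protocol and an analysis plan cannot repair it, so both points should be settled before the first patient is randomised.

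**What to change.** **CAP.** Do the baseline Fibroscan at enrolment, or at the allocation visit before the random number is assigned. State that CAP above 263 must be confirmed on that scan before allocation, and use the same scan as the efficacy baseline. Amend 4.5, 4.6, 5.5 and Table 2 to agree. The allocation-visit option needs no change to the Table 2 columns, only a sentence fixing the order.

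**Population.** Reconcile the title and synopsis, 2.1, 4.3 and 4.3.1 on whether type 2 diabetes is required, and reword the *or* clause so that it has one meaning. Which condition applies is for the sponsor to decide. Limit the conclusion to the population actually enrolled.

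**Cost.** This is a wording and schedule amendment. No patient who is randomised needs an extra scan, and 4.3 says the hospital already has a Fibroscan. The downside is scans in patients who then fail screening. To randomise 110 eligible patients, about 110 / 0.95 = 116 to 110 / 0.80 = 138 would be scanned under the assumed 5-20% shares, or 6 to 28 extra scans. Using the qualifying scan as baseline also means that part of any within-arm fall in CAP will be regression to the mean. That applies to both arms alike and leaves the between-group comparison intact.

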#### 4.3.2. Exclusion Criteria

- History of unsafe alcohol consumption
- Other liver disease (chronic viral/autoimmune/hereditary)
- Use of steatogenic medications
- History of drug dependence
- Body mass index (BMI) ≥35 kg/m2

28.02.2025

- A restrictive diet or weight change  $\geq 5$  kg during the 3 months prior to study
- Pregnancy or lactation
- Patients with sensitivity to caffeine intake
- Patients with symptomatic ischaemic heart disease, arrythmia's
- Any condition that, in the opinion of the clinician, would contraindicate the patient's participation.

## 4.4. Sample Size Calculation and Statistics:

#### Sample size(n)

$$n = \sigma 2(Z\alpha/2 + Z\beta)2/delta$$

where,

- $Z\alpha/2=1.96$  (for  $\alpha = 0.05$ , two-tailed test)
- $Z\beta=0.84Z$  {\beta} = 0.84 $Z\beta=0.84$  (for 80% power)
- $\sigma=5 \cdot sigma = 5\sigma=5$  (Standard Deviation)
- $\Delta=3$ \Delta =  $3\Delta=3$  (Expected Mean Difference)

#### Calculation,

Adjusting for Dropout (20%)

#### **Final Sample Size**

- 55 participants per group
- Total: 110 participants (both groups combined)

28.02.2025

## 4.5. Participant recruitment

• Participants will be recruited on a voluntary basis after obtaining informed written consent from patients with NAFLD by one of the investigators.

#### Patient Selection: Screening and eligibility assessment

- Advertisement about the details of the study and contact number of PI will display in all three languages (Sinhala/English/Tamil)at the Liver Clinic of Gastroenterology & Hepatology Department at CNTH-Ragama .Volunteering participants will contact PI and they will asked to come to Faculty medicine, University of Kelaniya, and they will approach by a trained medically qualified research assistant. First, the patients will be provided detailed information about the study and will be given an opportunity to discuss their concerns/questions in their preferred language (Sinhala/English/Tamil) with the medical investigator.
- Once the patient is satisfied with the information given, he/she will be screened for eligibility to participate in the trial. Informed written consent will be obtained from all patients with ultrasonically proven fatty liver disease for the eligibility assessment.
- All consenting patient's eligibility assessment for inclusion and exclusion criteria will be recorded in CRF by RA and reviewed by medical investigator in the team.
- Patients complied with inclusion exclusion criteria will be recruited to study and patients
  who are not eligible will be directed to Liver Clinic of Gastroenterology & Hepatology
  Department at CNTH-Ragama to receive standard care of treatment.

#### 4.6. Data collection:

- Data collection will be done by a two MBBS qualified graduates, who can converse in Sinhala, English and Tamil and are trained by the consultant hepatologist.
- An interviewer administered questionnaire will be used to record basic demographic details of the patient in addition to the data on clinical features. Patient identification data is collected for the purpose of tracing the patient in an adverse event or a medical

28.02.2025

- emergency. However, personal identification will not be used in the database, and the serial numbers will be used instead of names.
- Data collection will be done using a Case Report Form developed by the investigators.
   During each monthly visit, investigators will query regarding any adverse effects. Patients will also undergo clinical examination on visits.

#### History

A detailed clinical history will be taken regarding the basic demographic details such as
age, gender marital status, selected socioeconomic variables, relevant family history,
relevant past medical history, drug history, allergic history and consumption of alcohol
and tobacco will be recorded in CRF

#### **Anthropometric measurements**

Height, weight and waist circumference will be measured, and BMI will be calculated.
 All anthropometric measurements will be made by trained personnel. This will be done to check the eligibility for the study, at baseline and each monthly follow up visit.

#### Clinical examination

• Seated blood pressure is to be recorded on two occasions after at least a 10-min rest. A full physical examination will include head, ears, eyes, nose, mouth, skin, heart and lung examinations, lymph nodes, gastrointestinal, musculoskeletal, and neurological systems. This will do for checking the eligibility to the study, at baseline and each monthly follow up visit.

#### Laboratory investigations

Serum fasting plasma glucose, Lipid profile, Liver enzymes will be done to assess the
baseline fasting blood glucose for recruitment into the study to comply with inclusion
criteria. Serum HCG will be tested for female participants to exclude pregnancy.
Abdomen ultrasound scan will be performed to assess eligibility to the study.

28.02.2025

After recruitment baseline testing will be done for HbA1c, serum Insulin level, fasting
plasma glucose, Lipid profile, Liver enzymes. Serum creatinine, full blood count, serum
electrolytes and urine analysis will be done for safety assessments.

#### Ultrasound and Fibro scan

At the baseline Ultrasound scan will be performed to confirm the diagnosis of NAFLD.
 After recruitment at the baseline and at the end of six months a fibro scan will be done to assess the efficacy parameters. The ultrasound and fibro scan will be done at North Colombo Teaching hospital

#### Collection of blood samples

• Table 1 summarizes the blood sample collection. The investigations will be done at the North Colombo Teaching hospital which is an accredited laboratory. These tests are required to assess the efficacy and safety of the medications in an objective manner.

Table 1: Summary of Blood Sample Collection

Day	Blood volume	Investigations
Enrolment	6 ml	FBS, Liver profile  Lipid profile, Serum HCG (Female participants only)
Allocation Visit - Beginning of 1 st Month	6 ml	FBS Serum HbA1c Fasting serum insulin

28.02.2025

		Lipid profile, Liver profile, Total bilirubin
		Serum creatinine
		FBC
		Serum electrolytes
3 rd month and 6 th month	6 ml	FBS
		Serum HbA1c
		Fasting serum insulin
		Lipid profile, Liver profile, Total bilirubin
		Serum creatinine
		FBC
		Serum electrolytes

## 4.7. Randomization, blinding and code breaking

This is a Quadruple-blind study and either the Participant, Care Provider, Investigator, Outcomes Assessor will be aware of treatment assignments prior to the final database locks at the conclusion of the study.

Computer-generated random numbers will be used for randomization. Both caffeine tablets and placebo tablets will be packed into identical white HDPE (High Density Polyethylene) plastic bottles numbered from 1 to 110 by a pharmacist or an independent third party. according to the list of computer-generated random numbers. After packing each bottle according to this list with either Caffeine tablets or placebo tablets, the list will be placed in a sealed envelope until completion of the trial. The label of each bottle will indicate only the patient's random number and the direction

28.02.2025

for taking the tablets. This number will be clearly noted on each patient's CRF forms and tablets would be provided hence.

The caffeine and placebo tablets will be manufactured in identical shape and size and will be film coated to give the same appearance.

Bottles containing 60 caffeine tablets will be issued on day of allocation and will contain medication required for 30 days. The packed and sealed bottles will be stored at the University of Kelaniya, Faculty of Medicine, under recommended storage conditions specified by the manufacturer and kept under lock and key and released in small batches to be given to patients. Therefore, all investigators and patients will be blinded.

The codes can be accessed any time and in the event of a Serious Adverse Effect(SAE) or a Serious Adverse Reaction(SAR) the code of that patient will be broken. All eligible participants are randomly assigned to the two groups according to patient recruitment order.

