## 5. Intervention, Monitoring of compliance to treatment

Caffeine tablets and placebo tablets required for the trial would be sourced from Nutricost, a U.S.-based company that specializes in high-quality dietary supplements. Nutricost products are manufactured in GMP-compliant facilities and undergo third-party testing to ensure purity and consistency. The caffeine tablets specifically contain caffeine anhydrous, a dehydrated form of caffeine that provides a standardized and effective dosage and placebo are manufactured using starch ensuring that it is inert and does not affect the study's outcomes.

The study groups will receive one bottle on the day of allocation, and it will contain either caffeine tablets or placebo required for a month. The test group will receive the caffeine tablet while the control group will receive the placebo .Tablet bottles will be issued to participants according to their random number mentioned in the Case Report Form (CRF).

Patients will be asked to take the medication every day after dinner. Recommended dose and directions for use will be given verbally when dispensing the tablet pack, and written instructions will be clearly mentioned on the label of the bottle in Sinhala, Tamil and English. The patients will be asked to take the tablets home. At each monthly visit, the participants will be asked to bring tablet bottles with balance tablets, to count at the monthly visit to assess compliance. The required tablets for next month will be issued during this visit.

Participants who have < 80% compliance will be re-educated on the importance of daily administration of investigational product, as much as possible: with the overall aim to maintain  $\ge$  80% compliance over the study period.

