#### **5.2.** Dietary measurements

All patients will be instructed on a balanced diet, including decreased intake of saturated and trans fats and increased intake of fiber. In overweight patients, dietary intervention will focus on a calorie restricted diet, attained over a 6-month period. The calorie-restricted diets will be planned to create a deficit of 500- 1000 kcal/day and will be individualized for each study subject. A culturally validated Food Frequency Questionnaire (FFQ) will be used to obtain habitual intake of calories, macronutrients and micronutrients. This will be assessed monthly to monitor dietary measurements of participants.

Medical RA will meet individual patients for counselling on dietary intervention. All patients are asked to maintain food logs and ask to bring it on follow up visits and food logs will be reviewed monthly, and diet plans will be adjusted as needed.

Dietary measurements will be monitored at the baseline and during each follow up monthly visits.

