## **6.3.** Fair participant selection

Fair participant selection will be ensured through objective inclusion criteria, avoiding unjustified exclusions. Randomization balanced key characteristics, minimizing bias.

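### The CAP and LSM comparison ignores overweight status, which decides who gets the calorie-restricted diet, and section 4.7 does not say how 55 per group or six blinded monthly issues are secured

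*Protocol*

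**What the plan says.** - **Allocation (Protocol 4.7).** The method is given as "Computer-generated random numbers will be used for randomization", with participants assigned in order of recruitment. No ratio, block rule, fixed total per arm or stratification factor is stated.
- **Arm size (4.4).** The target is "55 participants per group", 110 in total.
- **Balance (6.3).** The ethics section states as a fact: "Randomization balanced key characteristics, minimizing bias".
- **Supply (4.7, 5 and Table 2).** Bottles numbered 1 to 110 are packed to the list, and the list is then sealed until completion. A bottle holds 60 tablets, enough for 30 days. One bottle is given at allocation, and for each monthly visit section 5 says: "The required tablets for next month will be issued during this visit". Table 2 marks study product at months 0 to 5, which is six issues.
- **Diet (5.2).** All participants get balanced-diet advice, but "In overweight patients, dietary intervention will focus on a calorie restricted diet, attained over a 6-month period", with a planned deficit of 500 to 1000 kcal/day.
- **Analysis (4.8).** Mean change in CAP and LSM is compared between arms by an independent t test or a Mann-Whitney test. No baseline covariate is used.

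**The concern.** Three things do not join up.

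First, the arm sizes and the balance claim rest on an allocation method that, as described, secures neither.

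Second, one sealed list and one numbered set of 30-day bottles do not supply months 2 to 6. The protocol does not say who packs the later bottles, or when, relative to sealing the list.

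Third, overweight status decides who gets a calorie-deficit diet. Section 5.1 calls lifestyle modification the focus of current treatment, so this diet can be expected to act on CAP and LSM. The protocol's own rule therefore makes overweight status a known baseline source of variation in the primary endpoints, and the analysis in 4.8 leaves that variation in the error term.

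At stake are some precision and a blinded supply procedure that can be carried out as written. The validity of the comparison is not at stake.

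**Working it through.** **1. The plan's own figure.** Inputs from 4.4: alpha 0.05 ("two-tailed test", Z = 1.96), 80% power (Z = 0.84), "Standard Deviation" 5, "Expected Mean Difference" 3, dropout 20%. The standard two-sample formula gives

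n = 2 × 5² × (1.96 + 0.84)² / 3² = 2 × 25 × 7.84 / 9 = 43.6, so 44 per group; 44 / 0.8 = 55.

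The figure reproduces. (The formula as it reads in 4.4 lacks the factor 2 and the square on the difference. It would give 25 × 7.84 / 3 = 65.3.) The standardised difference is 3/5 = 0.6. The protocol does not say which endpoint the 5 and the 3 belong to.

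**2. Arm sizes if the list were unrestricted.** With one arm distributed as Binomial(110, 0.5):

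| Event | Probability |
|---|---|
| Exactly 55:55 | 7.6% |
| Gap of 10 or more (60:50 or worse) | 39% |
| Gap of 20 or more (65:45 or worse) | 7.0% |

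**3. What unequal arms cost.** Take 80% completing, a standardised difference of 0.6 and the noncentral t distribution. Precision depends on n1·n2/(n1 + n2).

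| Randomised | Completing | n1·n2/(n1 + n2) | Power |
|---|---|---|---|
| 55:55 | 44/44 | 22.0 | 79.5% |
| 60:50 | 48/40 | 21.8 | 79.1% |
| 65:45 | 52/36 | 21.3 | 78.1% |

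The loss at 65:45 is 79.5 − 78.1 = 1.4 points. Averaged over all splits (normal approximation), power falls only from 80.4% to 80.0%.

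**4. Chance imbalance in overweight status.** The protocol gives no overweight share, so assume p = 0.5 to 0.85. With 55 per arm, SE = √(2p(1 − p)/55).

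| p | SE | P(arms differ by 10 points or more) |
|---|---|---|
| 0.50 | 0.095 | 29% |
| 0.70 | 0.087 | 25% |
| 0.85 | 0.068 | 14% |

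If overweight participants' change differs from the others' by an assumed 0.5 SD, a 10-point imbalance moves the contrast by 0.10 × 0.5 = 0.05 SD, against a planned 0.6 SD.

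**5. What adjustment gains.** If overweight status shifts change by s SD, it explains R² = p(1 − p)s² of the variance. The standardised difference becomes 0.6/√(1 − R²). With 44 per arm and one degree of freedom spent on the covariate:

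| p | s | R² | Power |
|---|---|---|---|
| 0.50 | 0.3 | 0.0225 | 80.4% |
| 0.50 | 0.5 | 0.0625 | 82.0% |
| 0.85 | 0.3 | 0.0115 | 79.9% |
| 0.85 | 0.5 | 0.0319 | 80.7% |

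Unadjusted power is 79.5%, so the gain is about 0.4 to 2.5 points.

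**6. Supply.** Six issues to 110 participants need 110 × 6 = 660 bottles, or 660 × 60 = 39,600 tablets. One bottle per number gives 110 × 60 = 6,600, one sixth of that.

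**The case against.** A reader might infer that 4.7 cannot deliver 55 per group. The text does not support that. Computer-generated random numbers may equally be used to permute a fixed list of 55 and 55, and 4.4 states that target. The 7.6% and 39% figures hold only for an unrestricted list, which remains a valid design.

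A reader might also infer that re-supply breaks the blind. That is not shown either. Labels carry the participant's random number and bottles are issued by that number, so 1 to 110 can be read as participant codes with several bottles behind each. On that reading the one-sixth shortfall disappears. Even if the list were consulted, the packer is a pharmacist or independent third party and not one of the blinded roles in 4.7.

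Chance imbalance in overweight status is not bias. The same diet rule applies in both arms, and the standard error of the t test already reflects that variation. Block sizes and strata are often left to a separate randomisation plan, and the sentence in 6.3 is loose wording in an ethics section.

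All of this stands, and it limits the point. What remains is that 4.8 commits to an unadjusted comparison despite a known source of variation. In addition, 4.7 and 5 do not state the one step, packing all bottles before sealing, that makes them fit together.

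**Conclusion.** The point holds as a modest precision gain and a clarification.

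- **Analysis.** Leaving overweight status out of the primary comparison forgoes roughly 0.4 to 2.5 points of power. This assumes a shift of 0.3 to 0.5 SD in change, an overweight share of 50% to 85%, and the planning values of 4.4. The protocol gives neither of the first two figures.
- **Arm sizes.** The method is unspecified rather than wrong. The power cost stays under about 1.5 points for splits up to 65:45.
- **Supply.** The described packing fits six monthly issues only if several bottles are packed per number before sealing, and the protocol does not say so. This is a gap in procedure and no evidence of unblinding.
- **Balance claim.** Section 6.3 asserts achieved balance that no described feature of the allocation secures. This is a wording matter.

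**What to change.** 1. **Section 4.8:** analyse CAP and LSM change with a linear model containing treatment and either baseline overweight status or baseline BMI. If status is used, define its cut-off in advance, since 5.2 gives none. Sections 4.6 and 5.5 already plan baseline anthropometry, so this costs nothing. Table 2, as it reads here, marks height and weight only from month 1 and should be checked against those sections.
2. **Section 4.7:** state a 1:1 list in permuted blocks of random size, with the sizes withheld from site staff. Stratifying by overweight status is optional. It needs the same cut-off, and because stratum sizes are unknown it also needs spare numbers and surplus packed bottles.
3. **Sections 4.7 and 5:** state that the independent pharmacist packs and labels six bottles per random number (660 in all) before the list is sealed. The tablets are needed in any case, so the cost is one earlier packing run.
4. **Section 6.3:** replace the claim of achieved balance with a statement that randomisation balances characteristics on average.

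Items 2 and 3 must be settled before the list is generated and the first bottle is packed.
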